6.1.8 Study Intervention Compliance

When the individual dose for a participant is prepared from a bulk supply, the preparation of the dose will be confirmed by a second qualified member of the study site staff.

When participants are dosed at the site, they will receive study intervention directly from the investigator or designee, under medical supervision. The date and time of each dose administered in the clinic will be recorded in the source documents and recorded in the CRF. The dose of study intervention and study participant identification will be confirmed at the time of dosing by a member of the study site staff other than the person administering the study intervention.

When compliance of less than 70% or more than 120% of the expected number of doses of study intervention is suspected, the reason for non-compliance with the dosing regimen should be documented in the dosing log of the participant's case report form, and should be reported as a protocol deviation and unless there is a protocol stipulated reason for non-compliance with the dosing regimen, this should be recorded as a dosing error.

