#### 6.4.3. Study Intervention Compliance

- Actual Dosing Days (ADY) is defined as the total number of dosing days on which study drug was administered.
- Exposure Time is defined as the total number of days from first to and including last day of study dosing (Last Oral Dosing Date - First Oral Dosing Date + 1);
- Dose Compliance is defined as the number of doses of study drug the subject took out of the expected total number of doses of study drug
  - ADY1 = Date of returning to clinical baseline – Date of first dosing (Day 1) + 1
  - Expected Doses (by mg):

(a)  $ADY1 \geq 14$ , Expected Doses =  $14 * 20 \text{ mg} = 280 \text{ mg}$ ;

(b)  $ADY1 < 14$ , Expected Doses =  $ADY1 * 20 \text{ mg} + (14 - ADY1) * 10 \text{ mg} = (140 + 10 * ADY1) \text{ mg}$ ;

- Dose Compliance =  $(\text{Total Actual Doses} / \text{Expected Doses}) * 100\%$

The continuous endpoints of actual Dosing Days, exposure Time, total actual doses and dose Compliance will be summarized as described in Section 5.2.2 by treatment group based on SAS as defined in Section 4.

Number and percent will be reported for subjects in Actual Dosing Days categories ( $\leq 7$  days, 8 ~ 13 days, 14 days), and Dose Compliance categories ( $< 70\%$ ,  $70\% \sim 130\%$ ,  $> 130\%$ ).

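### SAP 6.4.3 defines dose compliance as a count of doses but computes it as a ratio of milligrams over two dose levels, so some participants would fall on a different side of 70% than under protocol 6.1.8 (minor)

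*SAP*

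**What the plan says.** SAP section 6.4.3 gives the definition in words: "Dose Compliance is defined as the number of doses of study drug the subject took out of the expected total number of doses". The denominator it then sets out is labelled "Expected Doses (by mg", and it depends on ADY1, which runs from the first dose to the "Date of returning to clinical baseline". It is 280 mg if ADY1 is 14 or more. Otherwise it is 20 mg for each day up to ADY1 plus 10 mg for each remaining day, which the SAP simplifies to 140 + 10 × ADY1 mg. Dose Compliance is total actual doses over this figure, as a percentage, classed as below 70%, 70% to 130%, or above 130%.

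Protocol section 6.1.8 calls for a documented reason and a deviation report when there is suspected "compliance of less than 70% or more than 120% of the expected number of doses of study intervention". That is a limit on a number of doses. SAP section 2.1 declares only one departure from the protocol's analysis plan, the removal of hypothesis testing. It does not mention a change in the unit of compliance.

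**The concern.** The words and the formula in SAP 6.4.3 use different units, and the protocol's limit follows the words. In the mg ratio a dose weighs 10 mg before step-down and 5 mg after it, so a missed later dose costs half as much as a missed earlier one. Both phases also go into one total, so surplus mg from a missed step-down can make up for doses never taken.

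The half-weighted phase is the one likely to be taken at home. The protocol's Dose Rationale and SAP 2.3 expect discharge soon after return to clinical baseline with the remaining tablets in a bottle, whereas on-site doses are supervised under protocol 6.1.8. At stake is whether the reported compliance percentage and its class mean what the SAP says they mean, and whether the 70% figure shared by the two documents measures the same thing.

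**Working it through.** **Inputs.**
- 10 mg twice daily, then 5 mg twice daily, 14 days in total (protocol 6.1.2, SAP 2.3).
- Scheduled doses: 2 × 14 = 28. This is derived; neither document states it. It applies to the standard schedule.
- Expected mg, E = 20 × ADY1 + 10 × (14 − ADY1) for ADY1 below 14 (SAP 6.4.3).
- Total actual doses are taken to be in mg. The SAP does not say so, but a count over a mg denominator would give a fully adherent participant with ADY1 of 14 only 28/280 = 10%.

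**Reproducing the SAP figure.** 20 × ADY1 + 140 − 10 × ADY1 = 140 + 10 × ADY1, and 14 × 20 = 280. The SAP's expected-mg arithmetic is correct.

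**Three patterns under both measures.**

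| Pattern | By mg (SAP formula) | By count (SAP words, protocol 6.1.8) |
|---|---|---|
| ADY1 = 8, all doses to Day 8, none after | 8 × 20 = 160; 160/220 = 72.7% | 16/28 = 57.1% |
| ADY1 = 4, three full days missed before step-down | 180 − 60 = 120; 120/180 = 66.7% | 22/28 = 78.6% |
| ADY1 = 4, never stepped down, stopped after Day 9 | 9 × 20 = 180; 180/180 = 100% | 18/28 = 64.3% |

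The first two show disagreement at 70% in both directions. The third shows two opposite errors offsetting exactly.

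**How wide the disagreement is, with correct step-down and whole missed days.**
- Five days missed after step-down: count = 18/28 = 64.3%. By mg, (90 + 10 × ADY1)/(140 + 10 × ADY1) is at least 70% when 3 × ADY1 ≥ 8. With at least five days left to miss, that is ADY1 = 3 to 9.
- Six days missed after step-down: count = 16/28 = 57.1%. By mg, at least 70% when 3 × ADY1 ≥ 18, so ADY1 = 6 to 8.
- The entire post-step-down phase missed: mg = 20 × ADY1/(140 + 10 × ADY1), at least 70% from ADY1 = 8; count = ADY1/14, below 70% up to ADY1 = 9. The class reverses only at ADY1 = 8 or 9. At 7 both are below (140/210 = 66.7%; 50.0%); at 10 both are above (200/240 = 83.3%; 71.4%).

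**Missed step-down.** With every dose at 10 mg, the mg ratio is exactly 100% after (140 + 10 × ADY1)/10 = 14 + ADY1 doses. By count that is (14 + ADY1)/28: 53.6% at ADY1 = 1, rising to 67.9% at ADY1 = 5, and 71.4% or more from ADY1 = 6.

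**The case against.** **The same section already shows missed days.** Actual Dosing Days, Exposure Time and total actual doses are also summarised. When whole days are missed, the count ratio equals Actual Dosing Days/14: the three patterns give 8/14, 9/14 and 11/14, all in the 8 to 13 day class. This stands. A reader might infer that the compliance percentage is the only planned evidence on whether the regimen was taken, and the SAP does not support that. These outputs nevertheless do not show a missed single dose, assign mg to a phase, or correct the percentage and its class.

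**A dose could mean a 5 mg tablet.** Protocol 6.1.1 identifies the study intervention as 5 mg tablets, and a tablet ratio equals the mg ratio (280/5 = 56 tablets), so words and formula would agree. But protocol 6.1.2 speaks of a 10 mg dose given twice daily, and 6.1.8 records a date and time for each dose, which describes an administration. Even on the tablet reading, a missed step-down still offsets missed doses.

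**Weighting by mg is legitimate, and a count has its own blind spot.** Someone never stepped down who misses nothing scores 28/28 = 100% by count but 280/180 = 155.6% by mg at ADY1 = 4. This stands, and it is why the mg ratio should be kept alongside the count.

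**The patterns are narrow.** Two of the three stop before Day 14, exact offsetting needs one particular number of doses at each ADY1, and neither document says how often such patterns occur. This also stands, although the second pattern in the table and the five-day and six-day results do not require early stopping.

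**The table and the deviation record have different purposes.** A reader might infer that they are bound to identify different participants. The SAP reports counts by class and does not claim to reproduce the deviations, and the protocol rule is triggered by suspicion. Disagreement is possible for some patterns; it is not inevitable.

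**Conclusion.** The inconsistency is real and minor. SAP 6.4.3 computes something other than what it defines, and its 70% class is not on the same scale as the protocol's 70% limit. Some patterns are classed differently, in either direction, and a missed step-down can mask missed doses.

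The effect is confined to a descriptive compliance table. A reader might infer that efficacy conclusions are at risk, and the documents do not support this: SAP 5.1 has no hypothesis testing, neither analysis set in SAP section 4 uses compliance, and the estimand in SAP 2.2.1 keeps all observed data. SAP section 7 records a review after 24 randomisations and no later enrolment, so if 24 is the final number, one reclassified participant is 1/24, about 4% of those randomised.

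The conclusion assumes that a dose is an administration, that 28 are scheduled, and that total actual doses are in mg. The patterns are possible ones, not observed ones.

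**What to change.** In SAP 6.4.3, compute Dose Compliance as doses taken over doses expected, as its own definition and protocol 6.1.8 say, state that a dose is one administration, and apply the 70% class to that ratio. Keep mg taken over mg prescribed as a separate dose-intensity line, split before and after return to clinical baseline, so that a missed step-down stays visible and cannot cancel missed doses. State the unit of total actual doses and the nominal mg given to a placebo tablet, which the mg line needs and the count does not. SAP 6.4.3 and protocol 6.1.8 should then be reconciled.

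No dosing rule changes. The cost is a wording change, one derived variable from dosing data already in use, and an extra dose-intensity line in the exposure table.

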 - Known active tuberculosis or history of inadequately treated tuberculosis;
 - Known HBV, HCV, or HIV.

Prior/Concomitant Therapy:

Have received any of the following treatment regimens specified in the timeframes outlined below:

Within 4 weeks prior to the first dose of study intervention:

- Prior treatment with any JAK inhibitors, potent immunosuppressants, or any biologic agents including IL-6 inhibitors (eg, tocilizumab) or IL-1 inhibitors (eg, anakinra) within the past 28 days or 5 half-lives, whichever is longer.
- Prior treatment with any potent cytochrome P450 inducer, such as rifampin, within the past 28 days or 5 half-lives, whichever is longer.

Within 48 hours prior to the first dose of study intervention:

• Treatment with herbal supplements.

Received >/= 20 mg/day of prednisone or equivalent for >/=14 consecutive days in the 4 weeks prior to screening

Diagnostic Assessments:

- Severe hepatic impairment, defined as Child-Pugh class C.
- Severe anemia (hemoglobin <8 g/dL).
- ANY of the following abnormalities in clinical laboratory tests at screening, confirmed by a single repeat, if deemed necessary:
 - WBC <1000/mm3
 - Absolute lymphocyte count <500 cells/mm³;
 - Absolute neutrophil count <1000 cells/mm³.
- Alanine transaminase/aspartate transaminase (ALT/AST) > 5 times the upper limit of normal;
- Estimated glomerular filtration rate (eGFR) < 40 mL/min/1.73 m2);

Other Exclusions:

- Known allergy to tofacitinib.
- Investigator site staff or Pfizer employees directly involved in the conduct of the study, site staff otherwise supervised by the investigator, and their respective family members.
- Enrollment in another clinical trial to study COVID-19

Treatment Considerations

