6.1.2 Dosage, Administration, Schedule

TREATMENT DESCRIPTION

Tofacitinib or placebo will be administered. Tofacitinib will be administered in a dose of 10 mg PO BID until return to their clinical baseline (as defined by supplementary oxygen requirement), and then will continue to be administered at 5 mg PO BID for a total treatment duration of 14 days. Follow-up off tofacitinib will continue up to Day 90.

- Tofacitinib tablets will be sourced from Pfizer, Inc. Matching placebo tablets will be provided by Pfizer, Inc..
- Participants will swallow the study intervention whole and will not manipulate or chew the study intervention prior to swallowing. If the participant is unable to swallow the study intervention whole, tofacitinib 5 mg film-coated tablets will be disintegrated in water (in a syringe) and administered as a liquid suspension through a nasal-gastric (NG) tube or percutaneous endoscopic gastrostomy (PEG) tube. Dosing of the suspension should occur within 4 hours from the time of preparation, when stored at room temperature (15-25°C), or within 24 hours, when at refrigerated temperature (2-8°C). Dosing verification was completed by Pfizer which was demonstrated through in-use stability of the prepared

suspension, compatibility of the suspension with common materials of composition for NG and PEG tubes, and accuracy of the intended dose. Since tofacitinib meets the Biopharmaceutics Class System (BCS) criteria for high solubility designation and the 5 mg IR tablet has been demonstrated to be bioequivalent to 5 mL of the oral solution (1 mg/mL) (Study A3921354 conducted under IND 117,400), we expect that disintegration of the 5 mg tablet in the syringe will not adversely impact the bioperformance.

• Study intervention administration details will be recorded on the CRF.

Intervention Name	Tofacitinib
ARM Name	Tofacitinib plus SoC therapy
Туре	Drug
Dose Formulation	Tablet
Unit Dose Strengths	5 mg
Dosage Level	10 mg BID
Route of Administration	Oral or per nasogastric tube
Use	Experimental
IMP or NIMP	IMP
Sourcing	Provided by Pfizer
Packaging and Labeling	Study intervention will be provided in bottles with appropriate
	labeling.
Current/Former Names or Aliases	CP-690550, Xeljanz [®]

REQUIRED TREATMENT MODIFICATIONS

The following dose adjustments need to be considered during the use of 10 mg BID in this patient population when the potential exists for differences in tofacitinib exposure due to DDI or changes in renal or hepatic function:

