- When a concomitantly used drug is a strong CYP3A4 inhibitor, OR when a co-administered drug is both a moderate CYP3A4 inhibitor and a strong CYP2C19 inhibitor (eg, fluconazole), a 50% reduction in dose is recommended. Therefore, a 5 mg BID dose should be used to achieve a similar exposure as that of 10 mg BID in a patient not receiving co-administered metabolic inhibitor.
 - Antivirals such as lopinavir and ritonavir are examples of potent CYP3A4 inhibitors. Cobicistat, which is used to increase concentrations of antiviral drugs, is also a potent CYP3A4 inhibitor. Examples of other co-administered drugs requiring dose reduction are ketoconazole, itraconazole, clarithromycin, telithromycin, and fluconazole (**Appendix 2**).
 - Tofacitinib dose reduction is not needed when co-administered with the following medication: azithromycin, hydroxychloroquine, chloroquine, remdesivir, favipiravir, oseltamivir, and ribavirin.
- A 50% dose reduction is recommended in patients who are in moderate or severe renal impairment (including patients on hemodialysis) and those in moderate hepatic impairment. Therefore 5 mg BID should be used in these patients, which will be

changed to 5 mg PO QD upon return to their clinical baseline (as defined by supplementary oxygen requirement).

- Tofacitinib should not be used in patients with severe hepatic impairment (Participants with Child-Pugh class C are excluded).
- Tofacitinib use is not recommended in patients receiving a potent CYP3A4 inducer (eg, rifampin, St. John's wort) or if they had discontinued use of a potent CYP3A4 inducer less than 28 days or 5 half-lives prior to the first dose of tofacitinib.

Required Tofacitinib Discontinuations:

In rare instances, it may be necessary for a participant to permanently discontinue study intervention (definitive discontinuation). Reasons for definitive discontinuation of study intervention include the following.

- WBC count <1000 /mm3
- Lymphocyte counts <250 cells/mm3.
- Absolute neutrophil counts <500 cells/mm3.
- Hemoglobin less than 8 g/dL.
- ALT or AST ≥5 times the ULN.
- Anaphylaxis or other serious allergic reaction.
- Diagnosis of venous thromboembolism.
- Any serious infection, including secondary bacterial pneumonia, or other safety event for which the investigator determines that continued treatment with tofacitinib is not in the participant's best interest.

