 - Antivirals such as lopinavir and ritonavir are examples of potent CYP3A4 inhibitors. Cobicistat, which is used to increase concentrations of antiviral drugs, is also a potent CYP3A4 inhibitor. Examples of other co-administered drugs requiring dose reduction are ketoconazole, itraconazole, clarithromycin, telithromycin, and fluconazole (**Appendix 2**).
 - Tofacitinib dose reduction is not needed when co-administered with the following medication: azithromycin, hydroxychloroquine, chloroquine, remdesivir, favipiravir, oseltamivir, and ribavirin.
- A 50% dose reduction is recommended in patients who are in moderate or severe renal impairment (including patients on hemodialysis) and those in moderate hepatic impairment. Therefore 5 mg BID should be used in these patients which will be changed to 5 mg PO QD upon return to their clinical baseline (as defined by supplementary oxygen requirement).
- Tofacitinib should not be used in patients with severe hepatic impairment (Participants with Child-Pugh class C are excluded).
- Tofacitinib use is not recommended in patients receiving a potent CYP3A4 inducer (eg, rifampin, St. John's wort) or if they had discontinued use of a potent CYP3A4 inducer less than 28 days or 5 half-lives prior to the first dose of tofacitinib.

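### SAP 6.4.3 measures dose compliance against the unmodified regimen for every patient, so full adherence to a protocol-prescribed dose reduction can score as low as 50%

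*SAP*

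**What the plan says.** SAP 6.4.3 describes dose compliance as the "number of doses of study drug the subject took out of the expected total number of doses of study drug", and computes it in mg. Expected mg is 20 mg per day up to return to clinical baseline and 10 mg per day after that, over 14 days. This gives 140 + 10 × ADY1 for ADY1 below 14, and 280 mg otherwise. Patients are then counted as below 70%, 70% to 130%, or above 130%.

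The protocol prescribes or allows lower doses in three situations:

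- **Renal or hepatic impairment (6.1.2, 6.1.11).** Patients with moderate or severe renal impairment or moderate hepatic impairment receive 5 mg BID, "changed to 5 mg PO QD upon return to their clinical baseline". Section 6.1.11 repeats this: "which will be changed to 5 mg PO QD upon return to their clinical baseline".
- **CYP inhibitors (6.1.2, 6.1.11).** The bullet reads: "Therefore, a 5 mg BID dose should be used to achieve a similar exposure as that of 10 mg BID in a patient" who is not taking the inhibitor.
- **Suspected toxicity (3.2.1, toxicity monitoring).** The dose may be lowered to 5 mg BID.

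Such patients can be on study. The hepatic exclusion in 5.3.2 is "Severe hepatic impairment, defined as Child-Pugh class C" (with ALT/AST above 5 times the upper limit), so moderate hepatic impairment is not excluded. The renal exclusion is "Estimated glomerular filtration rate (eGFR) < 40 mL/min/1.73 m2". The lead-in to the modifications in 6.1.2 also foresees "differences in tofacitinib exposure due to DDI or changes in renal or hepatic function" during treatment.

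Protocol 6.1.8 flags suspected compliance below 70% as a deviation, to be recorded as a dosing error "unless there is a protocol stipulated reason for non-compliance with the dosing regimen". SAP 6.4.3 uses the same 70% cut without that exception.

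**The concern.** A compliance percentage should compare what was taken with what was prescribed. Here the numerator follows the patient's actual regimen, but the denominator is fixed at the full one. The below-70% category therefore mixes missed doses with correct dosing at a reduced level. The error also runs the other way: a patient who should have been reduced and was not appears perfectly compliant.

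SAP version 2.0 is descriptive only, so its tables are its whole output. SAP 7 says that the first safety review took place after 24 subjects were randomised and that no more were enrolled. In arms of that size, one misplaced patient is visible.

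**Working it through.** **Inputs.** Full regimen and expected mg: SAP 6.4.3. Reduced regimens: protocol 6.1.2, 6.1.11 and 3.2.1. ADY1 is not reported, so it is varied from 1 to 14.

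**Step 1: reproduce the SAP denominator.** E = 20 × ADY1 + 10 × (14 − ADY1) = 140 + 10 × ADY1. At ADY1 = 14 this is 280 mg, which matches the SAP.

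**Step 2: renal/hepatic reduction from Day 1, every dose taken.** R = 10 × ADY1 + 5 × (14 − ADY1) = 70 + 5 × ADY1 (140 mg if ADY1 ≥ 14). R/E = (70 + 5 × ADY1)/(140 + 10 × ADY1) = 50% at every ADY1. To reach the 70% to 130% band, this patient would have to take 0.70 × E/R = 140% to 1.30 × E/R = 260% of the prescribed mg.

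**Step 3: the same patient wrongly given the full regimen.** The score is E/E = 100%, although the patient took E/R = 2 times the prescribed mg.

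**Step 4: 5 mg BID for all 14 days with a CYP inhibitor, every dose taken.** The amount taken is 14 × 10 = 140 mg, so the score is 140/(140 + 10 × ADY1). A reduction to 5 mg BID for toxicity from Day 1 gives the same figures.

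| ADY1 | Expected mg (SAP) | Renal/hepatic mg, score | 5 mg BID for 14 days, score |
|---|---|---|---|
| 1 | 150 | 75, 50.0% | 93.3% |
| 3 | 170 | 85, 50.0% | 82.4% |
| 5 | 190 | 95, 50.0% | 73.7% |
| 6 | 200 | 100, 50.0% | 70.0% |
| 7 | 210 | 105, 50.0% | 66.7% |
| 10 | 240 | 120, 50.0% | 58.3% |
| 14 | 280 | 140, 50.0% | 50.0% |

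The last column is below 70% from ADY1 = 7.

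**Step 5: renal/hepatic reduction that starts mid-course.** The daily dose is halved from the start day on. The table gives the latest start day that still scores below 70%, and the score one day later.

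| ADY1 | Latest start below 70% | Score | Score one day later |
|---|---|---|---|
| 3 | Day 4 | 115/170 = 67.6% | 120/170 = 70.6% |
| 5 | Day 4 | 125/190 = 65.8% | 135/190 = 71.1% |
| 7 | Day 5 | 145/210 = 69.0% | 155/210 = 73.8% |
| 10 | Day 5 | 160/240 = 66.7% | 170/240 = 70.8% |
| 14 | Day 6 | 190/280 = 67.9% | 200/280 = 71.4% |

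**Step 6: weight of one patient in the table.** With 24 randomised and all assumed dosed, one patient is 1/12 = 8.3% of an arm at 1:1 (protocol 5.1), or 1/16 = 6.3% and 1/8 = 12.5% at 2:1 (SAP 2.3).

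**The case against.** The strongest reply is that little depends on this table and that the reader has other information. SAP 6.4.3 also reports actual dosing days, exposure time and total actual dose, so a reduced patient who completes treatment still appears in the 14-day category. Concomitant drugs are summarised in SAP 6.4.4. Dosing errors are judged separately under protocol 6.1.8, with its exception for protocol-stipulated reasons, and SAP 6.4.3 labels nobody as a dosing error. The affected group may be empty: eGFR below 40 is excluded, the protocol gives no cut-off for moderate renal impairment, and CYP inhibitors are to be avoided where possible. All of this stands and limits the size of the point. It does not make 50% the right score for a patient who took every prescribed dose.

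It can also be said that correcting the denominator will not make the below-70% category a pure measure of missed doses. The denominator always spans 14 days, so required stops (thrombosis, serious infection, laboratory limits, rescue therapy) and deaths before Day 14 also lower the score. That is true, and the table should say so.

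A reader might go further and infer that the protocol leaves open which dose a CYP-inhibitor patient takes after return to baseline, because only the renal/hepatic bullet names a second step. The documents do not support this. The lead-in in 6.1.2 and 6.1.11 ties the adjustments to the use of 10 mg BID. The CYP bullet names 5 mg BID as the replacement, and 5 mg BID is already the general dose after baseline. Where a further step to 5 mg QD was intended, under the same lead-in, it was written out. The natural reading is 5 mg BID throughout. A QD step for these patients would be a new dosing choice, and rewording the protocol after enrolment ended would change nobody's dose.

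**Conclusion.** The point holds as a minor error in the SAP. The formula in 6.4.3 does not deliver the measure that the section defines once a patient is on a prescribed or permitted reduction. A renal/hepatic patient reduced from Day 1 scores exactly 50% at every ADY1. A patient on 5 mg BID for all 14 days scores from 93.3% at ADY1 = 1 down to 50.0% at ADY1 = 14.

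These figures assume that every prescribed dose was taken and, outside Step 5, that the reduction ran for the whole course. Whether renal patients could be affected at screening depends on an assumed boundary for moderate impairment above eGFR 40. Hepatic patients, and patients whose renal or hepatic function changes on treatment, do not depend on that assumption. The documents do not give the number of affected patients.

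The effect is confined to the dose-compliance summary. A reader might infer that the efficacy results are compromised, but compliance defines no analysis set in SAP 4 and SAP 5.1 tests no hypotheses.

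**What to change.** In SAP 6.4.3, define Expected Doses as the sum of each patient's prescribed daily mg:

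- unmodified regimen: 140 + 10 × ADY1 mg (280 mg if ADY1 ≥ 14), as now;
- renal/hepatic reduction throughout: 70 + 5 × ADY1 mg (140 mg if ADY1 ≥ 14);
- days on a CYP inhibitor, or on a toxicity reduction to 5 mg BID: 10 mg per day;
- a modification that starts or stops mid-course: a day-by-day sum.

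A patient who takes every prescribed dose then scores 100% at any ADY1. Add a footnote that protocol-required discontinuations also lower the score, because the denominator spans 14 days.

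The cost is one revised definition, one footnote and the matching programming. Administration details, tablets per patient and concomitant medications are already recorded (protocol 6.1.2, 6.1.6, 6.1.8 and 6.1.11). No protocol amendment, new data or extra visit is needed.
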